#### **4.2 Recruitment process**

Potential patients and caregivers will be approached by study staff of the Penn State Hershey ALS center at the time they are seen for routine visits to the Penn State Hershey ALS Clinic. In addition, a letter will be sent via mail or email to patients of the Penn State Hershey Medical Center ALS clinic, as well as those who are registered with the Greater Philadelphia chapter of the ALS Association. A flyer will be posted in the clinic area informing patients of the study. Interested individuals will respond to a member of the study team who will follow up as in Section 4.4.

Practice control participants will be recruited from clinical staff by members of the study team.

Respiratory therapists will be approached by study staff prior to their first rPFT administration so that they may be delivered the SER and give verbal consent.

#### **4.3 Recruitment materials**

Potential patient participants may be mailed (see “Recruitment Letter” in Recruitment Materials) or emailed (see “Email Recruitment Letter” in Recruitment Materials) a recruitment letter. There will also be a flyer for the study posted within the clinic area (see “Study Flyer” in Recruitment Materials).

#### **4.4 Eligibility/screening of subjects**

Before enrolling prospective participants, we will contact the potential participant team by phone, email, or in person. For those individuals who are Hershey Medical Center patients, we will ask for their consent to access their medical record to confirm certain inclusion and exclusion criteria. For potential participants who are not treated at the Hershey Medical Center, we will request that they release medical records to us from their doctor. These will be reviewed by the study physician to confirm the diagnosis of ALS and other inclusion/exclusion criteria.

We will confirm that they and their caregiver are aware of the study requirements and are willing to complete the study procedures according to the procedures described (see “Screening questionnaire” in recruitment materials). This form addresses the remaining inclusion and exclusion criteria. In it, we will ask the patient if they anticipate any issues relating to performing spirometry or lack inadequate internet access to participate (in the case of Part 2). The participant team will be directed to an online internet speed test to ensure sufficient connection speed. We also ask if the caregiver anticipates they will be able assist in administering the procedure.

Eligibility of respiratory therapists will be determined by their role in the Hershey Medical Center ALS clinic as well as their verbal consent to participate in the study.

## **5.0 Consent Process and Documentation**

### **5.1 Consent Process**

#### **5.1.1 Obtaining Informed Consent**

##### **5.1.1.1 Timing and Location of Consent**

A member of the study team will review the informed consent documents with the participants and receive their written consent to participate in the study. This consent procedure will take place only after all screening procedures have been completed. This will take place either at the Hershey Medical Center ALS clinic, over the phone, or using the telemedicine interface between the clinic and the patient’s home.

A member of the study team will deliver the summary explanation of research (SER) to participating respiratory therapists before their first clinical interaction in this study. The SER will be delivered at the Hershey Medical Center ALS Clinic.

#### **5.1.1.2 Coercion or Undue Influence during Consent**

Patients will be informed that the treatment they receive for ALS will not be affected by their choice to participate in the study. Explanation of the study and obtaining consent will be performed by a member of the research team who is not part of the clinical care team.

#### **5.1.2 Waiver or alteration of the informed consent requirement**

Partial waiver of consent is requested for pre-screening purposes.

### **5.2 Consent Documentation**

#### **5.2.1 Written Documentation of Consent**

We will verify that we are using the most current IRB-approved version of the study specific consent form and that the consent form is in language understandable to the subject. A copy of the consent form will be provided to the subject. Whenever possible, the consent form will be provided to the subject in advance of the consent discussion.

A member of the research team will review the informed consent documents with the prospective participants and receive their written consent to participate in the study described in this protocol. If performed over the phone or telemedicine interfaces. Participants will sign a physical copy of the form and mail/email it to the research team. The patient and the caregiver from the prospective participant team will sign their own consent forms. This consent procedure will take place either in the ALS Clinic or over the telemedicine interface between the clinic and the patient's home. Written documentation of consent will be delivered after participants have been given an overview of the study's goals, procedures, risks, and benefits. Participants will receive a copy of the consent after it has been signed and dated by the person explaining the study.

#### **5.2.2 Waiver of Documentation of Consent (Implied consent, Verbal consent, etc.)**

Verbal consent will be obtained by the respiratory therapist participant before their first study session.

Verbal consent will also be obtained by participants via telephone to ask screening questions.

### **5.3 Consent – Other Considerations**

#### **5.3.1 Non-English Speaking Subjects**

Non-English speaking subjects will not be enrolled.

#### **5.3.2 Cognitively Impaired Adults**

##### **5.3.2.1 Capability of Providing Consent**

The physician investigator will determine whether an individual is capable of providing informed consent. Cognitively impaired patients will not be enrolled in this study.

Due to disease progression, some subjects may not be able to physically sign the consent form, regardless of cognitive status thereby requesting LAR signature.

### **5.3.2.2 Adults Unable To Consent**

The procedure outlined in HRP 013, “SOP: Legally Authorized Representatives, Children, and Guardians” will be followed to determine the legally authorized representative capable of providing informed consent. Written informed consent from the subject’s LAR will be obtained before any study procedures take place.

### **5.3.2.3 Assent of Adults Unable to Consent**

Subjects who are unable to sign the consent will be asked to provide verbal assent, which may be provided using an assistive communication device.

## **5.3.3 Subjects who are not yet adults (infants, children, teenagers)**

### **5.3.3.1 Parental Permission**

N/A

### **5.3.3.2 Assent of subjects who are not yet adults**

N/A

## **6.0 HIPAA Research Authorization and/or Waiver or Alteration of Authorization**

### **6.1 Authorization and/or Waiver or Alteration of Authorization for the Uses and Disclosures of PHI**

**Check all that apply:**

- Not applicable, no identifiable protected health information (PHI) is accessed, used or disclosed in this study. [Mark all parts of sections 6.2 and 6.3 as not applicable]**
- Authorization will be obtained and documented as part of the consent process. [If this is the only box checked, mark sections 6.2 and 6.3 as not applicable]**
- Partial waiver is requested for recruitment purposes only (Check this box if patients' medical records will be accessed to determine eligibility before consent/authorization has been obtained). [Complete all parts of sections 6.2 and 6.3]**
- Full waiver is requested for entire research study (e.g., medical record review studies). [Complete all parts of sections 6.2 and 6.3]**
- Alteration is requested to waive requirement for written documentation of authorization (verbal authorization will be obtained). [Complete all parts of sections 6.2 and 6.3]**

### **6.2 Waiver or Alteration of Authorization for the Uses and Disclosures of PHI**

#### **6.2.1 Access, use or disclosure of PHI representing no more than a minimal risk to the privacy of the individual**

##### **6.2.1.1 Plan to protect PHI from improper use or disclosure**

Information is included in the “Confidentiality, Privacy and Data Management” section of this protocol.

#### **6.2.1.2 Plan to destroy identifiers or a justification for retaining identifiers**

The identifiers collected in the study and stored on REDCap will be maintained until the completion of the study, including analysis, and dissemination of results. Email addresses and phone numbers may be retained for those participants who are interested in participating in future research studies.

#### **6.2.2 Explanation for why the research could not practicably be conducted without access to and use of PHI**

Certain PHI is used to maintain contact with the research subject through phone, mail, or email. Other PHI are variables related to the analysis of the study, such as age, diagnosis, gender, and ALSFS-R scores. Social security numbers are collected for payment purposes.

#### **6.2.3 Explanation for why the research could not practicably be conducted without the waiver or alteration of authorization**

In order to be able to screen participants, we will need to access their medical record, either through the Hershey Medical Center EMR or through the release of records from an external care provider. We will access patients' medical records for the purpose of confirming the diagnosis of ALS before we admit them into the study and obtain consent. In order to contact patients, to describe the study and schedule the study visit, we will need access to phone numbers and email. Additionally, in the case of Study 2, we will need to know the patient's address to be able to ship the rPFT kit.

### **6.3 Waiver or alteration of authorization statements of agreement**

Protected health information obtained as part of this research will not be reused or disclosed to any other person or entity, except as required by law, for authorized oversight of the research study, or for other permitted uses and disclosures according to federal regulations.

The research team will collect only information essential to the study and in accord with the 'Minimum Necessary' standard (information reasonably necessary to accomplish the objectives of the research) per federal regulations.

[figure not shown]
Access to the information will be limited, to the greatest extent possible, within the research team. All disclosures or releases of identifiable information granted under this waiver will be accounted for and documented.

## **7.0 Study Design and Procedures**

### **7.1 Study Design**

Part 1: This is a self-controlled study where each participant will be administered a standard of care PFT for measurement of FVC and MIP, as well as an rPFT, separated by at least an hour, for measurement of experimental FVC and MIP. The rPFT is guided by a respiratory therapist in another room, utilizing the telemedicine interface of the Hersey ALS clinic and devices for measuring FVC and MIP (**Error! Reference source not found.**).

Part 2: This is a randomized controlled study to determine whether regular monitoring of respiratory function at monthly, rather than every 3-month intervals, over the course of a year, can lead to better

**Figure 2: (A) Image of the telemedicine interface used by the Hershey ALS clinic. (B) The rPFT toolkit. From left to right: The GiO 4 respiratory pressure meter and mouthpiece, smartphone running the spirometry application, and Air Smart Spirometer and turbine.**

patient outcomes. In the experimental group, standard FVC and MIP measurements obtained by the respiratory therapist in the ALS clinic every 3 months are supplemented with telemedicine-guided rPFT performed at monthly intervals (**Error! Reference source not found. 1**). Controls receive standard PFT assessments only. Patient outcomes, NIV recommendation, quality of life, and survival over one year, will be compared between experimental and control groups.

The researcher and respiratory therapist will be present either in person or virtually for all study sessions and will guide the patient and caregiver in the appropriate use of the equipment. Two devices are used to measure two aspects of respiratory function:

1) Air Smart Spirometer, Pond Healthcare Innovation AB

The following information is paraphrased from the user manual, which is included in the “devices” page of the protocol.

“Air Smart Spirometer is intended to measure the forced expiratory volume in 1 sec (FEV1) and the forced vital capacity (FVC) in a forced expiratory maneuver. These measures can be used for the detection, assessment and monitoring of certain lung diseases. The Air Smart Spirometer is intended to be used by:

- Healthcare professionals trained to perform spirometry tests on patients.
- Adults trained by healthcare professionals or through self-learning who understand how to perform a high quality spirometry test.

The Air Smart Spirometer works with iPhone and connects via its cable to the headphone input jack. The Air Smart Spirometer has a built-in battery designed to function for at least 2 years or 1 000 single tests. When the battery is drained, dispose of the device as electronic waste. The Air Smart Spirometer is designed to work with disposable and single use FlowMir® turbines. When performing a spirometry test, the user exhales into the turbine. The airflow generated sets a rotor in motion. The Air Smart Spirometer registers the speed of the spinning rotor, converts it and transfers the data to the smartphone with the Air Smart Spirometer app.”

2) GiO 4 Digital Pressure Gauge, Respiralogs

The following information is paraphrased from the user manual, which is included in the “devices” page of the protocol.

“GiO Pressure Gauge is a high accuracy digital gauge that displays pressure measurement in both analog bar and digital reading. The GiO Gauge can be used in various settings and has a wide range of

applications in both medical and non-medical fields. GiO Digital Pressure Gauge is designed to detect and display pressure reading to a high degree of accuracy. This means it may also be sensitive to changes in pressure and is so fast in responding to the changes that you may find it difficult to determine the reading you would like to record. The P&H or Peak and Hold function is a design that captures and holds the display of peak pressure reading. The GiO 4 measures pressures from -60 cm H2O to 0 cm H2O."

During each rPFT administration, the respiratory therapist will guide the patient and caregiver through three valid maneuvers of the FVC and MIP tests. The therapist informs the caregiver to prepare the spirometer by connecting it to the tablet and opening the associated application. The patient is told to sit as upright as possible for the measurement of FVC. They will be told that to do this they will 1) inhale maximally, 2) exhale as hard and fast as possible, and 3) continue to exhale until indicated by the therapist. The therapist will also demonstrate this procedure to the patient. The caregiver applies nose clips to block airflow through the nose, holds the turbine of the spirometer to the patient's mouth and performs three repetitions of this sequence, with periods of relaxation between testings. Testing is repeated further until the therapist is satisfied with three valid maneuvers. The application on the tablet computes the FVC and percentage predicted value using the NHANES III criteria [Hankinson1999]. The largest FVC from a valid run is recorded.

To perform the MIP test, the therapist instructs the patient to breathe normally. The caregiver turns on the GiO pressure meter and attaches the mouthpiece, which is placed in the mouth of the patient. The patient is told they will be asked to draw breath in as quickly and powerfully as possible, for at least one second. The therapist tells the caregiver to place a finger over the valve outlet so that no air flows through the mouthpiece during inhalation. Nose clips will be used. As the therapist instructs, the patient performs three repetitions of this task, noting the reading each time. The maximal negative pressure from a valid run is recorded.

Each piece of reusable equipment will be labeled with an identification number. A log of all loaned materials will be maintained by the researchers. This log, included in the supporting documents, will be maintained on REDCap. Before delivery of the system to the study participant, the each piece of equipment will be inspected and tested. This study will not collect prior medical therapy relevant to the use of the device. There are no restrictions on medicines or therapies used by the participants in this study.

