### **3.2 Exclusion Criteria**

#### Part 1

Patients:

- 1) Cognitive impairment, as judged by the ALS clinic neurologist, that prevents participation in the study.
- 2) ALS Functional Rating Scale (ALSFRS-R) [Cedarbaum1999] score on day of screening of less than or equal to 2 on all of the items for speech, swallowing, and salivation. These items are indicators of bulbar dysfunction, which limits the reliability of PFT administration.

Caregivers: None

Controls: None

Respiratory Therapists: None

Part 2 imposes additional exclusion criteria for patients only.

Patients:

- 3) Use of NIV or diaphragm pacer at time of obtaining informed consent.
- 4) FVC  $\leq$ 50% predicted or MIP  $>$  -60 cm H2O.

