### **8.2 Sample size determination**

Our sample size is predetermined based on our subjective ability to recruit patients within the time frame of the study. Power analysis was based on studies of FVC decline. Lo Coco et al., [LoCoco2006], showed that 50% of study participants dropped below 50% predicted FVC in one year. Given that our exclusion criteria for Part 2 will reject many of the 37% of individuals in their study who were "slow progressors," we estimate that 75% of patients enrolled in our study will meet the respiratory criteria to recommend NIV. This results in a sample size per arm of n=15, which provides 80% power to detect a difference in mean outcome between the two groups if the effect size is found to be 0.95.

Assuming a monthly change in FVC of  $3.5 \pm 3.4\%$  found by Schiffman et al. [Schiffman1993], we conducted 10,000 Monte-Carlo simulations of 40 participants declining at this rate for 12 months. Half were sampled once every three months, and half were sampled every month.  $80.6 \pm 6.3\%$  of simulated participants met the requirements for NIV recommendation, in roughly equal proportions across groups. The average FVC at recommendation was 47.0% predicted in the experimental group, and 43.4% predicted in the control group. The effect size of the difference in FVC between groups was  $.964 \pm .343$ . Similarly, the two measures of QoL obtained at NIV recommendation are powered with an 80% chance to detect improvement of quality of life in the experimental group if the effect size is also found to be 0.95. This corresponds to a mean score difference of 1.52 on the SAQLI, assuming a standard deviation of 1.6 [Flemons1998]. Although there is no published data on the standard deviation of MDRS-D scores, the range and format of questions is similar enough to estimate a comparable difference between groups is needed.

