### **8.3 Statistical methods**

Part 1: The primary hypothesis is that there is no difference in the results of PFT and rPFT for respiratory assessment of FVC and MIP. We will use a paired sample t-test to determine if the mean test results are comparable between the standard and experimental treatments. We will conduct a qualitative analysis to determine whether the patient, caregiver, and therapist determine the rPFT to be an effective way to conduct tests of breathing function.

Part 2: The primary outcomes will be analyzed to determine if respiratory parameters are closer to the actionable threshold at NIV recommendation and whether QoL is better sustained at this point in individuals in the experimental group. This will be done using a non-parametric two sample test of means, the Wilcoxon-Mann-Whitney rank sum test.

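### In Part 2, FVC at NIV recommendation may be read on the home device in one arm only, and the recorded arm difference does not follow a home-clinic offset; an offset-corrected sensitivity analysis should be prespecified.

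*Combined protocol and SAP*

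**What the plan says.** Section 7.1 sets the measurement schedule of Part 2. The experimental arm's clinic tests "are supplemented with telemedicine-guided rPFT performed at monthly intervals". For the other arm, "Controls receive standard PFT assessments only". Section 7.2.2 counts five clinic tests and eight home tests over the year, so after month 0 an experimental patient has eight home and four clinic readings. The same section lets every session end with a therapist's recommendation based on that session's results, reviewed by the neurologist.

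Section 7.1 says that the home application gives a "percentage predicted value using the NHANES III criteria". No reference equation is given for the clinic test, and the clinic spirometer is not named.

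Section 8.3 asks whether "respiratory parameters are closer to the actionable threshold at NIV recommendation" in the experimental arm, using a rank-sum test. It has no device term, offset correction or device sensitivity analysis. Part 1 compares the two procedures in 40 teams with a paired t-test, but no rule carries its estimate into Part 2.

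The Section 8.2 simulation separates the arms only by sampling interval: "Half were sampled once every three months, and half were sampled every month".

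**The concern.** The instrument is partly aligned with the arm: a control's outcome always comes from the clinic test, whereas an experimental patient's may come from either. A systematic difference between devices would then enter the arm comparison.

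The stopping rule makes this hard to see. A patient is recommended at the first reading at or below 50, and that reading is the outcome. If the home device reads high, the patient is recommended later, at a lower FVC on the clinic scale, but the recorded value still sits just under 50. A stable recorded difference therefore gives no assurance that the clinic-scale difference is stable.

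What is at stake is what the primary FVC result can support. Section 1.1 claims that recommendation comes closer to the initiation criteria, and a high-reading home device could remove much of that gain while the recorded contrast looks much as planned. QoL is read at the same point, so its date shifts too.

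**Working it through.** **Inputs from Section 8.2.** "Assuming a monthly change in FVC of" 3.5 ± 3.4 points; "10,000 Monte-Carlo simulations of 40 participants declining at this rate for 12 months"; monthly against three-monthly sampling.

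**Assumptions.** Section 8.2 gives no baseline FVC. I use Normal(80, 8), kept above 50, and check against a fixed 82. The documents give no home-clinic offset δ, so I take -5 to +5 points, constant, on home readings only.

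**Model.** FVC falls each month by an independent Normal(3.5, 3.4) draw. Controls are read at months 3, 6, 9 and 12. Experimental patients are read every month, with δ added except at those four months. Recommendation is the first reading ≤ 50.

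**Reproducing the plan's figures (δ = 0).**

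| | Plan | Rebuilt, Normal(80, 8) | Rebuilt, fixed 82 |
|---|---|---|---|
| Mean FVC, experimental v control | 47.0 v 43.4 | 47.04 v 43.44 | 47.04 v 43.47 |
| Effect size | 0.964 ± 0.343 | 0.964 ± 0.340 | 0.957 ± 0.343 |
| Recommended | 80.6 ± 6.3% | 80.7 ± 6.3% | 81.0% |

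**Adding the offset (baseline Normal(80, 8)).** A home-triggered reading equals clinic-scale FVC + δ, so:

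clinic-scale difference = recorded difference - δ × (share of experimental recommendations triggered at home).

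| δ | Home share | Recorded difference | Clinic-scale difference |
|---|---|---|---|
| -5 | 93.1% | 2.92 | 2.92 + 5 × 0.931 = 7.58 |
| -3 | 84.6% | 3.29 | 3.29 + 3 × 0.846 = 5.83 |
| 0 | 64.3% | 3.60 | 3.60 |
| +3 | 40.8% | 3.14 | 3.14 - 3 × 0.408 = 1.92 |
| +5 | 27.1% | 2.53 | 2.53 - 5 × 0.271 = 1.17 |

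The fixed baseline of 82 gives the same pattern (home share about 84%, 64% and 40% at -3, 0 and +3).

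**Closeness to the threshold.** The hypothesis concerns distance from 50, so the signed difference misleads when δ is negative. At -5, about 66% of experimental recommendations have a clinic-scale FVC above 50 (mean 51.0). With absolute distance from 50 (fixed baseline 82), the gain over control is about 3.9 at -5, 4.4 at -3 and 3.6 at zero. For positive δ every triggering value is below 50 on both scales, so the gain equals the signed difference: about 1.9 at +3 and 1.2 at +5. Relative to no offset, 1.92/3.60 = 0.53 (about half lost) and 1.17/3.60 = 0.33 (two thirds lost).

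**Effect on power.** Two-sided rank-sum power, 20 enrolled per arm, alpha 0.05 (assumed; the plan states neither alpha nor sidedness), is 63% at zero, 56% at -3, 49% at +3, 42% at -5 and 32% at +5.

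**Timing.** The mean experimental month of recommendation moves from 7.2 at -5 to 8.7 at +5 (8.1 to 9.5 with the fixed baseline).

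**What Part 1 can supply.** With 40 pairs and a paired SD of 7 points (assumed), the 95% half-width is 2.02 × 7/√40 = 2.2 points. At SDs of 8 and 10, power to detect a 3-point offset is 64% and 46%, so a non-significant Part 1 test would not exclude offsets of this size.

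**The case against.** The recorded reading is a defensible outcome. The intervention is a home-monitoring strategy, device included, and the recommendation rests on the FVC measured at the session. That stands, and it is why the recorded comparison should stay.

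The offset is assumed. No section reports a home-clinic bias, and Part 1 exists to look for one. That also stands: nothing here shows that the home device is biased. But Part 1 has no agreement margin and no link to Part 2.

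A reader might infer more than the documents support:

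- That an offset could manufacture a positive result. Every offset tested lowered the recorded difference from its no-offset value of 3.6.
- That the recorded difference hardly moves whatever the offset. This fits offsets up to about 3 points (9-13% lower at ±3); at ±5 it falls by 19-30%.
- That experimental outcomes always come mostly from the home device. The share is below half once the device reads about 2 points high (49% at +2).
- That a low-reading device hides a doubled benefit (7.58 against 3.60 at -5). Most of those recommendations precede the criterion on the clinic scale; measured as closeness, the gain is about 3.9.
- That the clinic uses another reference equation. The text is silent, which is not evidence of a difference.

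Correction has limits too. Part 1 tests were done in another clinic room rather than at home, and in a broader population that includes PLS and PMA and has no FVC or NIV exclusion.

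**Conclusion.** The concern holds in limited form. Device is partly confounded with arm, and the threshold rule makes the recorded difference a poor guide to the clinic-scale one. Between offsets of -3 and +3 points the clinic-scale difference runs from about 5.8 to 1.9 while the recorded one stays at 3.1-3.6. The consequential direction is a home device that reads high. At +3 the recorded difference exceeds the clinic-scale one by 3.14 - 1.92 = 1.22 points, and about half of the planned gain is gone. The harm is a misdescribed gain and lost power.

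These sizes rest on an assumed baseline, an assumed constant offset and independent monthly declines. The dyspnea-with-MIP route to recommendation was not modelled. That the clinic and home spirometers differ is inferred from Part 1's purpose. A sensitivity analysis is warranted; replacing the primary comparison is not.

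**What to change.** In Section 8.3, keep the recorded comparison and prespecify beside it a sensitivity analysis of FVC at recommendation:

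1. Record which device produced each triggering reading.
2. Subtract the Part 1 mean rPFT-PFT difference from home-triggered readings and leave clinic readings unchanged.
3. Repeat at both limits of the Part 1 95% confidence interval.
4. Report the signed FVC and the absolute distance from 50 by arm.
5. Compute % predicted from litres with the same NHANES III equation for both devices.

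The cost is analysis wording and recoding; no visit, device or clinical rule changes. The correction carries its own error: with a half-width of 2.2 points and a 64% home share, the corrected difference moves by about 2.2 × 0.64 = 1.4 points either way, against an expected 3.6. State as limitations that the Part 1 offset was measured in a clinic room in a broader population, and that the correction cannot undo the shift in the date at which QoL is read.

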#### Part 1: Demonstrate the reliability of remote pulmonary function testing, performed via telemedicine, for monitoring respiratory function in patients with amyotrophic lateral sclerosis (ALS)

*Primary Hypothesis:* There is no difference in the results of PFT and rPFT for respiratory assessment of FVC and MIP.

*Secondary Hypothesis:* The respiratory therapist, patient, and caregiver will express confidence in conducting the rPFT, as determined by surveys of procedure acceptance.

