## **16.0 Resources Available**

### **16.1 Facilities and locations**

For Part 1, the consent procedure will be conducted within the ALS Clinic at [name] on the Hershey Medical Center campus. The clinic houses a room set up by the Penn State Hershey information technology department that is dedicated to ALS telemedicine. This room will also be used as the site for the respiratory therapist to conduct the rPFT assessment. This research room is in a private location and contains all the tools necessary for engaging in secure videoconferencing.

For Part 2, consent may be obtained in the ALS clinic or over the telemedicine interface. The home of the patient will be the site of most of the study procedures for the participant team. A member of the study team and the respiratory therapist will communicate with the participant team over the telemedicine interface in the research room of the ALS clinic.

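### Section 7.1 leaves room for the researcher to help with the equipment in person during the Part 1 rPFT, and nothing requires that help to be recorded

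*Combined protocol and SAP*

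**What the plan says.** The Part 1 aim in section 1.1 reads: "Demonstrate the reliability of remote pulmonary function testing, performed via telemedicine". The overall objective in the same section is guided testing in the home.

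Section 7.1 contains a general sentence on staffing that covers both parts: "The researcher and respiratory therapist will be present either in person or virtually for all study sessions and will guide the patient and caregiver" in operating the devices correctly. It names two people, gives both a guiding role, and leaves the mode of attendance open.

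The description of the Part 1 rPFT is more specific about the therapist: "The rPFT is guided by a respiratory therapist in another room, utilizing the telemedicine interface of the Hersey ALS clinic". Section 7.1 adds: "During each rPFT administration, the respiratory therapist will guide the patient and caregiver through three valid maneuvers of the FVC and MIP tests". On the devices it says: "The therapist informs the caregiver to prepare the spirometer by connecting it to the tablet and opening the associated application". The caregiver also applies the nose clips, holds the turbine to the mouth, turns on the pressure meter, attaches its mouthpiece and covers the valve outlet with a finger.

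Section 16.1 describes a dedicated telemedicine room in the clinic and says of Part 1: "This room will also be used as the site for the respiratory therapist to conduct the rPFT assessment". For Part 2 it says: "A member of the study team and the respiratory therapist will communicate with the participant team over the telemedicine interface".

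Section 8.3 compares mean PFT and rPFT results with a paired t-test. Section 7.2.1 has the dyad and the therapist complete a survey on ease of use and confidence after the procedures.

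**The concern.** A therapist on a video link can coach, but cannot seat a nose clip, hold a turbine or cover a valve outlet. In the home these tasks fall to the caregiver alone. A leak or an incompletely covered outlet can change the FVC or MIP reading, so whether the dyad manages the equipment unaided is part of what decides whether a home reading can be trusted.

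The general sentence in 7.1 lets a researcher sit with the dyad during a Part 1 rPFT and guide them on the equipment. If that happens, handling errors that would occur at home may be put right on the spot. The test result then moves closer to the clinic PFT, and the dyad and therapist may report more confidence than unaided use would have earned. Both effects favour the two Part 1 hypotheses. Part 2 then takes its interim readings, which feed the NIV recommendation described in section 7.2.2, without anyone in the room to give that help.

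Since no record of help is required, the analysis could not show afterwards whether this had happened.

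**Working it through.** The plan states no figure on this point, so the check is a comparison of what each section says about who guides the rPFT and from where.

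1. **Therapist, Part 1.** Fixed. Section 7.1 puts the therapist in another room on the telemedicine interface, and section 16.1 assigns the room. The therapist also coaches each maneuver and decides when three are valid.
2. **Caregiver, both parts.** Section 7.1 assigns the device handling to the caregiver, acting on the therapist's instruction. It gives the researcher no task in that procedure.
3. **Researcher, Part 2.** Section 16.1 puts a study team member on the telemedicine link alongside the therapist.
4. **Researcher, Part 1.** The only applicable statement is the general one in 7.1: present at every session, in either mode, with a guiding role on equipment. Section 16.1 is silent on the researcher's location in Part 1. Section 7.2.1 describes the researcher's part in consent but not in the rPFT.
5. **Cross-reference.** Section 7.2.1 sends the reader to section 7.4.2 for rPFT administration. In the text available, section 7 ends at 7.3, so this pointer does not settle the question.
6. **Record and analysis.** Neither section 7.2.1 nor section 8.3 provides for noting in-room help or for analysing assisted sessions separately.

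Items 1 and 2 show that remote coaching is tested and that the intended handler is the caregiver. Items 4 to 6 show that nothing prevents or captures researcher help with that handling in Part 1.

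On direction, suppose unaided handling shifts the rPFT by an average of b. Suppose also that a share s of sessions is helped, and that help removes a fraction c of the shift. The mean PFT-rPFT difference due to handling then has size

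b × (1 − s × c),

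which is smaller than b whenever s and c are above zero, and is zero when every session is fully corrected (s = c = 1). The documents give no value for b, s or c, so the direction can be stated but the size cannot.

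**The case against.** The strongest reply is that the general sentence has an ordinary meaning. It covers all sessions in both parts, including clinic PFTs and the month 0 survey, which is completed with a researcher present. Read that way, staff attend in person at clinic sessions and virtually at remote ones. The specific rPFT procedure gives the handling to the caregiver and the coaching to the therapist, so researcher help would depart from it. No section plans such help.

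Much of this stands. The point concerns what the wording permits, not a stated intention. But the benign reading is not written down, and a Part 1 rPFT takes place during a clinic visit, where attending in person is easy and arguably fits the words. The sentence also gives the researcher a guiding role, not merely an observing one.

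Three stronger readings are tempting, and the documents do not support them:

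- **That Part 1 need not test remote guidance at all.** Sections 7.1 and 16.1 make the therapist's guidance in Part 1 remote without exception.
- **That any session in the study could be helped in person.** Section 16.1 puts the study team member on the telemedicine link in Part 2, so the gap is confined to Part 1.
- **That the 3.6-point gap in section 8.2 (47.0 − 43.4) can stand in for the bias that help would hide.** That gap is a simulated difference in FVC at NIV recommendation between monthly and quarterly sampling. It says nothing about measurement error in unaided spirometry, so power figures built on it would not be evidence.

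**Conclusion.** The point holds, limited to equipment handling in the Part 1 rPFT. The plan gives the researcher a guiding role that may be exercised in person, does not say where the researcher is during that test, and does not require help to be recorded. Agreement seen in Part 1 could therefore partly reflect set-up help that home users will not have.

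The size is unknown. The direction, toward no difference and toward confidence, rests on two assumptions: that unaided handling errors shift readings on average, and that a person in the room would tend to correct them. Neither can be tested from the documents. The gap is worth closing because it touches the Part 1 primary hypothesis, the remedy is nearly free, and unlogged help cannot be reconstructed later.

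**What to change.** - **Section 7.1:** state that during Part 1 rPFTs, as section 16.1 already provides for Part 2, the researcher and therapist guide only through the telemedicine interface. Anyone in the room with the dyad observes without verbal or hands-on help, except for safety. The rule should bar help rather than presence, since silent observation poses little of this threat.
- **Session form:** add a field recording whether in-room help was given and what kind.
- **Section 8.3:** report the number of assisted sessions as rPFTs not completed remotely. Keep all sessions in the main PFT-rPFT comparison and survey summary. Show both with and without assisted sessions as a sensitivity analysis, noting that exclusion can itself favour agreement because it drops the sessions that went worst remotely.
- **Section 7.2.1:** correct the pointer to section 7.4.2.

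The cost is a few sentences and one form field, with no extra staff or visits. A few Part 1 sessions may fail that help would have rescued, but those failures are themselves information about remote feasibility.
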